### 10.0 MONITORING

It is the responsibility of St. Jude Medical as the sponsor of the study to ensure the study is conducted, recorded, and reported according to the approved protocol, subsequent amendment(s), applicable regulations, and guidance documents. Monitoring will be conducted according to the St. Jude Medical Clinical Monitoring standard operating procedure.

Prior to beginning the study, St. Jude Medical will contact the investigator or designee to discuss the study and data requirements. A St. Jude Medical monitor will periodically review the subject records and associated source documents.

The investigator shall make subject and study records available to the clinical monitor for monitoring.

### 11.0 REGULATORY INSPECTIONS

The investigator and/or delegate should contact St. Jude Medical immediately upon notification of a governmental agency inspection at the site. A clinical monitor or designee will assist the investigator and/or delegate in preparing for the audit.

An investigator who has authority to grant access will permit authorized governmental agency employees, at reasonable times and in reasonable manner, to enter and inspect any establishment

## Clinical Investigational Plan

where devices are held (including any establishment where devices are used or where records or results are kept).

An investigator, or any person acting on behalf of such a person with respect to the study, will permit authorized governmental agency employees, at reasonable times and in reasonable manner, to inspect and copy all records relating to the study.

An investigator will permit authorized governmental agency employees to inspect and copy records that identify subjects, upon notice that governmental agency has reason to suspect that adequate informed consent was not obtained, or that reports required to be submitted by the investigator, to the Sponsor or EC or IRB have not been submitted or are incomplete, inaccurate, false or misleading.

### 12.0 STATISTICAL CONSIDERATIONS

#### 12.1 STATISTICAL DESIGN, HYPOTHESES, METHOD AND ANALYTICAL PROCEDURES

A subset of subjects enrolled in this study will be used to meet the Post Market Clinical Follow-Up (PMCF) requirement for CE mark. Once this subset of subjects is enrolled and followed for 12 months and have evaluable endpoint data at the 3-month follow-up visit, a report pertaining to primary endpoint and secondary endpoints analyses will be submitted indicating completion of this requirement.

##### 12.1.1 Primary Endpoint

The proportion of subjects with a therapeutic window (evaluated by a blinded evaluator) which is larger under directional stimulation than omnidirectional stimulation will be tested against a performance goal of 60% at the 3-month follow-up visit.

The width of the therapeutic window is defined as the electrical current at which a sustained side effect appeared minus the electrical current at which a meaningful therapeutic benefit was obtained. The directional segment with the widest therapeutic window will be compared to omnidirectional stimulation.

#### Hypothesis

The hypothesis is formally expressed as:

$$H_0: p \leq 0.60$$

$$H_a: p > 0.60$$

where  $p$  is the probability that the therapeutic window under directional stimulation is larger than the therapeutic window under omnidirectional stimulation.

#### Analysis

The primary endpoint will be tested at the 5% significance level. The analysis population includes subjects who have evaluable therapeutic window using omnidirectional and directional stimulation. The analysis will be carried out by calculating the 95% lower confidence bound (LCB) on the success rate using the Clopper-Pearson exact method. The null hypothesis will be rejected if the 95% lower confidence bound (LCB) for  $p$  is greater than 0.60.

## Clinical Investigational Plan

### 12.1.2 Secondary Endpoint

#### 12.1.2.1 Secondary Endpoint 1

If the primary study endpoint is not met, the following hypothesis will be tested to evaluate non-inferiority of therapeutic window with directional stimulation compared to omnidirectional stimulation.

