A comparison of the therapeutic window using directional stimulation to the therapeutic window using omnidirectional stimulation will be performed for each lead on each subject. Subjects will be considered to have a greater therapeutic window with direction stimulation if one or both leads has a larger therapeutic window with directional stimulation than omnidirectional stimulation.

A blinded evaluator will be used in this study to minimize study bias. The blinded evaluator will assess the therapeutic window for each subject at initial programming, the 3-month visit and the 12-month visit. The UPDRS part III motor examination for each subject will also be assessed by the blinded evaluator at the 3-month and 6-month visits. The blinded evaluator will not be aware of the subject's programming or device settings at the time of the evaluation. In addition, subjects will be unaware of their programmed parameters for the first 6 months.

All serious adverse events (SAEs), serious procedure-related events (and procedure-related AEs lasting longer than 30 days) and device-related adverse events will be recorded throughout the subject's participation in the study.

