### 4.3.2 Secondary Objective

Demonstrate non-inferiority of the directional lead DBS therapeutic window to the omnidirectional lead DBS therapeutic window and comparison of UPDRS part III motor examination scores at 3 and 6 months to evaluate therapeutic differences in omnidirectional vs directional stimulation.

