### 4.4.2 Secondary Endpoint

If primary endpoint not met, the proportion of subjects with a therapeutic window (evaluated by a blinded evaluator) which is larger under directional stimulation than omnidirectional stimulation tested against a performance goal of 40% at the 3 month follow-up visit; Comparison of 3-month vs. 6-month UPDRS part III motor examination scores (evaluated by a blinded evaluator) to assess omnidirectional vs. directional stimulation.

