#### Hypothesis

The hypothesis is formally expressed as:

$$H_0: p \leq 0.40$$

$$H_a: p > 0.40$$

where  $p$  is the probability that the therapeutic window under directional stimulation is larger than the therapeutic window under omnidirectional stimulation (success).

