#### Analysis

The secondary endpoint will be tested at the 5% significance level. The analysis population includes subjects who have evaluable therapeutic windows under omnidirectional and directional stimulation. The analysis will be carried out by calculating the 95% lower confidence bound (LCB) on the success rate using the Clopper-Pearson exact method. The null hypothesis will be rejected if the 95% lower confidence bound (LCB) for  $p$  is greater than 0.40.

#### 12.1.2.2 Secondary Endpoint 2

The endpoint will test whether directional stimulation has greater therapeutic effect than omnidirectional stimulation by comparison of 3- and 6-month UPDRS part III motor examination (as evaluated by a blinded evaluator).

Change in UPDRS part III motor examination within each subject is defined as:

Change in UPDRS part III = UPDRS part III at 3 month (omnidirectional) – UPDRS part III at 6 months (directional)

The following hypothesis will be tested:

$$H_0: \text{mean change in UPDRS part III motor examination} \leq 0$$

$$H_a: \text{mean change in UPDRS part III motor examination} > 0$$

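### Secondary endpoint 1 is called non-inferiority of the therapeutic window, but it tests only whether more than 40% of subjects have a wider directional window and puts no limit on lost width

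*Combined protocol and SAP*

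**What the plan says.** - **Objective.** Section 4.3.2, like the synopsis, sets out to "Demonstrate non-inferiority of the directional lead DBS therapeutic window to the omnidirectional lead DBS therapeutic window".
- **When it is tested.** Section 12.1.2.1 applies only if the primary endpoint is not met: "the following hypothesis will be tested to evaluate non-inferiority of therapeutic window with directional stimulation compared to omnidirectional stimulation".
- **Parameter.** The null is p ≤ 0.40 against p > 0.40, where p "is the probability that the therapeutic window under directional stimulation is larger than the therapeutic window under omnidirectional stimulation (success").
- **Decision rule.** "The null hypothesis will be rejected if the 95% lower confidence bound (LCB) for" p is above 0.40, using the Clopper-Pearson exact method at the 5% level.
- **Scale of the window.** Section 12.1.1: "The width of the therapeutic window is defined as the electrical current at which a sustained side effect appeared minus the electrical current" giving meaningful benefit. It is a quantity in units of current.
- **Which directional reading.** Section 12.1.1: "The directional segment with the widest therapeutic window will be compared to omnidirectional stimulation". Section 4.4.1 says the same.
- **What counts as success.** Section 4.2 treats a subject as having a greater directional window "if one or both leads has a larger therapeutic window with directional stimulation than omnidirectional stimulation". Section 4.4.2 gives only the short form: "the proportion of subjects with a therapeutic window (evaluated by a blinded evaluator) which is larger under directional stimulation than omnidirectional stimulation".
- **Other uses of width.** Mean widths are compared as a descriptive endpoint (synopsis and 4.4.3), with no margin or hypothesis. Section 12.1 says that the post-market (PMCF) report will cover the primary and secondary endpoint analyses.

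**The concern.** A non-inferiority claim says that any loss is smaller than a stated amount. Here the quantity named in the claim is a width in current, but the statistic keeps only the sign of each subject's comparison. A subject who loses a trivial width and one who loses most of the window count the same. Under the either-lead rule, a subject counted as a success may also lose width on the other lead.

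The conclusion would be used when the primary has failed and readers turn to the fallback. A PMCF report stating that non-inferiority of the therapeutic window was shown would be taken to mean that directional stimulation is not materially worse in width. The test does not establish that.

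**Working it through.** **Inputs.** n = 66 (12.12); performance goals 0.60 and 0.40, one-sided 95% Clopper-Pearson lower bounds (12.1.1, 12.1.2.1); planned success rate 75% (12.2). The rest of 12.2 is redacted, so no stated power can be reproduced.

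**1. Which results carry the label.** For x successes the lower bound is the 5th percentile of Beta(x, n − x + 1).

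| Successes of 66 | Lower bound | Result |
|---|---|---|
| 33 | 0.3928 | fallback fails |
| 34 (51.5%) | 0.4075 | fallback passes |
| 46 | 0.5909 | primary fails |
| 47 | 0.6068 | primary passes |

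The fallback is therefore reached and passed with 34 to 46 successes.

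**2. What a pass shows.** A lower bound for p above 0.40 is the same as an upper bound below 0.60 for non-successes (losses plus ties). At 34 successes that bound is 1 − 0.4075 = 0.5925. No width enters the calculation.

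An illustration with assumed sizes: 34 successes of +0.1 mA and 32 losses of L give a mean difference of (34 × 0.1 − 32 × L)/66. This is −0.19, −0.43 and −0.92 mA for L = 0.5, 1.0 and 2.0 mA. All three pass. The sizes show what the rule permits and are not a forecast.

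**3. Where parity lies on the p scale.** Take three directional readings and one omnidirectional reading per lead, exchangeable and without ties. The chance that the widest directional reading exceeds the omnidirectional one is 3/4.
- Perfectly correlated leads: p = 0.75.
- Independent leads: p = 1 − (1/4)² = 0.9375.

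If the optional two-segment configurations in section 6.6 also count, there are six readings, and the values are 6/7 = 0.857 and 1 − (1/7)² = 0.980. Ties count as failures and lower all of these.

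**4. Can p exceed 0.40 when directional windows are narrower?** Assume independent normal readings with a common SD, and every directional segment truly narrower by d SDs. The widest of three then has mean −d + 0.846 SDs relative to omnidirectional.

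| d | Mean of widest segment | p, perfectly correlated leads | p, independent leads |
|---|---|---|---|
| 1.0 | −0.15 SD | 0.45 | 0.70 |
| 1.5 | −0.65 SD | 0.30 | 0.51 |

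At d = 1.0 even the widest segment is narrower on average, yet p is above 0.40 at both extremes of lead correlation.

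**5. How often the fallback is reached and passed.** P(34 ≤ X ≤ 46), X binomial(66, p):

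| True p | Probability |
|---|---|
| 0.75 | 0.195 |
| 0.70 | 0.52 |
| 0.65 | 0.81 |
| 0.60 | 0.90 |

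**6. How often that coincides with a demonstrable width loss.** Simulation with normal best-segment differences per lead (assumed), averaged over two leads: probability of 34 to 46 successes together with a 95% confidence interval for mean width wholly below zero.

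| True p | Perfectly correlated leads | Correlation 0.5 | Independent leads |
|---|---|---|---|
| 0.75 | 0 | 0 | about 0.02 |
| 0.60 | 0 | 0.26 | 0.88 |

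**The case against.** **The hypothesis is explicit, and non-inferiority on a win-probability scale is a recognised choice.** The null, threshold and method are indeed fully stated. But the label names the window, which the plan defines as a width. The natural reading of 40%, ten points below an even split, also fails here, because the study's success rule puts parity at 75% to 94% without ties.

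**The primary uses the same sign-only proportion.** This is true, and a primary pass bounds width loss no better. The mismatch is sharper for the fallback because non-inferiority is specifically a claim about the size of a possible loss.

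**Width is analysed anyway.** Mean widths are compared descriptively, and nothing excludes them from the PMCF report. That makes the remedy cheap, but a comparison without a margin does not turn the test into a non-inferiority test.

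**The practical weight is limited.** This stands. The test runs only after a failed primary, section 4.1 makes superiority the PMCF requirement, and section 12.3 says that no pass/fail criteria apply. The rejection rule and the objective remain in the text all the same.

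**The rationale for 40% may be redacted in 12.2.** It may be, and its absence is not counted here. No rationale for a threshold on p would bound lost width.

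**A reader might infer that 0.195 is the chance of a false reassurance about width.** The documents do not support that. It is the chance of reaching and passing the fallback. At the planned 75% rate, the chance of doing so with a demonstrable width loss is between 0 and about 0.02 under the assumed model.

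**Conclusion.** The point holds as a mismatch between label and test. Passing secondary endpoint 1 supports the statement that more than 40% of subjects meet the success rule. It does not support a claim that directional stimulation is not worse in window width. The label would attach to 34 to 46 successes of 66.

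The cut-offs and binomial probabilities are exact given n = 66. The 75% to 94% range assumes exchangeable readings, three segments, no ties, and that the widest-segment and either-lead rules apply to this endpoint. Section 12.1.2.1 does not restate those rules, but 4.2 gives a general definition of success, and 12.1.1 uses similar shorthand for the primary.

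Two stronger readings should be avoided. The documents do not show that directional windows are narrower, or that a width loss is likely at the planned rate. Nor can the 40% rule be converted into a margin in mA, since that needs reading error, step size and lead correlation, none of which is given.

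Severity lies between minor and low should-fix.

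**What to change.** 1. In the synopsis, 4.3.2 and 12.1.2.1, replace the non-inferiority wording with: *If the primary endpoint is not met, test the proportion of subjects with a wider directional window against 40%.*
2. In 12.1.2.1 add: *Rejection supports only that more than 40% of subjects meet the success rule. It does not support a claim that directional stimulation is not worse in window width.*
3. Beside this result in the PMCF report, give the month-3 paired mean width difference, directional minus omnidirectional, with its 95% confidence interval, taken from the mean comparison already planned in 4.4.3. Note that choosing the widest segment favours directional stimulation. Under the normal model in the working, the advantage is about 0.85 reading SDs for the widest of three when there is no true difference.

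The cost is wording and one extra line of reporting, with no new data, visits or subjects. The sponsor gives up the fallback non-inferiority claim. The added mean difference is descriptive and tilted towards directional stimulation, so it must be read with the note. Keeping a non-inferiority claim would require a pre-specified, justified width margin and a test of the paired difference.

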#### Hypothesis

The hypothesis is formally expressed as:

$$H_0: p \leq 0.40$$

$$H_a: p > 0.40$$

where  $p$  is the probability that the therapeutic window under directional stimulation is larger than the therapeutic window under omnidirectional stimulation (success).

#### Analysis

The secondary endpoint will be tested at the 5% significance level. The analysis population includes subjects who have evaluable therapeutic windows under omnidirectional and directional stimulation. The analysis will be carried out by calculating the 95% lower confidence bound (LCB) on the success rate using the Clopper-Pearson exact method. The null hypothesis will be rejected if the 95% lower confidence bound (LCB) for  $p$  is greater than 0.40.

#### 12.1.2.2 Secondary Endpoint 2

The endpoint will test whether directional stimulation has greater therapeutic effect than omnidirectional stimulation by comparison of 3- and 6-month UPDRS part III motor examination (as evaluated by a blinded evaluator).

Change in UPDRS part III motor examination within each subject is defined as:

Change in UPDRS part III = UPDRS part III at 3 month (omnidirectional) – UPDRS part III at 6 months (directional)

The following hypothesis will be tested:

$$H_0: \text{mean change in UPDRS part III motor examination} \leq 0$$

$$H_a: \text{mean change in UPDRS part III motor examination} > 0$$

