### Initial Programming Visit

Each site will perform their standard monopolar review of each lead to determine the best contact selection for the subject followed by:

**Omnidirectional Testing** – Assessment of the contact that has been selected as providing the best clinical benefit. Omnidirectional testing is defined as:

- Any of the contacts on a 4 channel lead (1-4); or
- All 3 segments (A, B, and C) are activated on contact 2 or 3 of the 8 channel lead; or
- Contact 1 or 4 active on the 8 channel lead

Each lead will be assessed by a blinded evaluator for first meaningful therapeutic effect followed by assessment of first sustainable side effects.

As the amplitude is increased by the programmer, the therapeutic effect on the motor symptoms will be based on the blinded evaluator's clinical judgement.

First meaningful therapeutic effect will be determined by the blinded evaluator's clinical judgement of the benefit seen for the subject's primary motor symptoms (i.e.; first benefit seen in at least one of the cardinal symptoms of PD (Tremor, Rigidity, or Bradykinesia or other).

Once first therapeutic effect is determined, the site will test for side effects. The amplitude will continue to be increased slowly by the programmer until the first sustainable side effect is observed by the blinded evaluator.

Side effects will be documented based on the determination of the blinded evaluator.

The width of the therapeutic window is defined as the electrical current at which a sustained side effect appeared minus the electrical current at which a meaningful therapeutic benefit was obtained.

Subjects are to be programmed and remain programmed in an omnidirectional configuration from the initial programming visit until the 3-month visit. If in the investigator's opinion, omnidirectional

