## Clinical Investigational Plan

configuration does not provide adequate therapy for the subject, the investigator may change the programming to allow the use of a directional configuration.

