## Clinical Investigational Plan

The width of the therapeutic window is defined as the electrical current at which a sustained side effect appeared minus the electrical current at which a meaningful therapeutic benefit was obtained.

At the conclusion of the 3-month visit, the site physician should select the directional program that provides the best clinical benefit for the subject based on the detailed device testing that was completed and the subject should remain programmed using a directional configuration until the 6-month visit. If in the investigator's opinion, the directional configuration does not provide adequate therapy for the subject, the investigator may change the programming to allow the use of an omnidirectional configuration. Subjects who are implanted with the 4 channel lead will only have the omnidirectional testing at the initial programming visit to determine therapeutic window and first side effect. At the 3-month visit these subjects will complete the omnidirectional testing, will have the programming parameters collected and will complete the visit evaluations.

**12-Month Visit - Device testing is to be completed with the subject in the Off Medication state.** Omnidirectional and directional testing will be repeated according to the instructions above.

**36-Month Visit - Device testing is to be completed with the subject in the Off Medication state.** Omnidirectional and directional testing will be repeated according to the instructions above.

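### Secondary endpoint 2 reads the month-3 to month-6 UPDRS III change as an effect of directional stimulation, but by plan mode and period coincide, so the test cannot separate them

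*Combined protocol and SAP*

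**What the plan says.** Section 12.1.2.2 states the aim as a comparison of modes: "The endpoint will test whether directional stimulation has greater therapeutic effect than omnidirectional stimulation by comparison of 3- and 6-month UPDRS part III". The change is the month-3 score, labelled omnidirectional, minus the month-6 score, labelled directional. The null hypothesis is rejected if the one-sided 95% lower confidence bound on the mean change, from a t-distribution, is above zero.

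Section 6.6 fixes the order of the modes:
- First period: "Subjects are to be programmed and remain programmed in an omnidirectional configuration from the initial programming visit until the 3-month visit". If therapy is judged inadequate, "the investigator may change the programming to allow the use of a directional configuration".
- Second period: "the subject should remain programmed using a directional configuration until the 6-month visit". Again there is an exception: "the investigator may change the programming to allow the use of an omnidirectional configuration".

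The analysis set for this endpoint, in section 12.8, requires complete month-3 and month-6 UPDRS III scores and nothing more. For the primary endpoint, section 12.1.1 says: "The analysis population includes subjects who have evaluable therapeutic window using omnidirectional and directional stimulation". Section 12.1 says of the PMCF subset that "a report pertaining to primary endpoint and secondary endpoints analyses will be submitted indicating completion of this requirement". Section 12.7 adds subgroup analyses in subjects actually omnidirectional at month 3 and directional at month 6, and in subjects enrolled at implant or after it.

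**The concern.** All subjects are planned to follow the same sequence, and no group stays on omnidirectional stimulation through month 6. Mode is therefore aliased with period. A positive mean change could come from directional stimulation, from time since implant, from the re-optimisation of settings at month 3, or from a change in medication. Section 6.2 and Table 1 schedule the PD medication record at baseline, month 12 and month 36, so that item cannot show a change between months 3 and 6.

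What is at stake is the conclusion drawn. This is the only hypothesis test of motor benefit in section 12, and it goes into the PMCF report. As worded, rejection would be read as superior therapeutic effect even if the improvement had another cause. Equally, a real benefit could be hidden by worsening over the same three months.

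**Working it through.** **1. Does any design feature separate mode from period?**
- Coin flip (6.6, 3-month visit): it sets the order of acute device tests within that visit. It does not set the order of the treatment periods.
- Blinding of evaluator and subject (4.2, 6.6): it limits rating bias. It does not prevent real change over time.
- Regression adjustment (6.11): it is written for the primary endpoint.
- As-programmed subset (12.7): it removes subjects who did not follow the planned sequence, but those who remain all have omnidirectional first and directional second. It also selects on the investigator's view of whether therapy was adequate.
- Enrolled-at-implant and after-implant subsets (12.7): they are a partial check on drift with time since implant. Drift common to both is invisible.

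None of these separates the two.

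**2. How far can drift move the test?** No power, effect size or SD for this endpoint is legible, so there is no plan figure to reproduce.

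Inputs from the documents: one-sided 5% t test (12.1.2.2); n = 66 (12.12), taken here as an assumption because section 12.8 defines this endpoint's set differently. The drift d, in SDs of the change score, is also assumed.

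Reject if mean/(SD/√n) > t(0.95, 65) = 1.669, that is, if the observed mean exceeds 1.669/√66 = 1.669/8.124 = 0.205 SD, whatever its cause. The rejection probability is P[T′(65, d√66) > 1.669], with T′ noncentral t.

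No mode effect, improvement from other causes:

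| d | d√66 | Rejection |
|---|---|---|
| 0 | 0 | 5.0% |
| 0.1 | 0.812 | 20.0% |
| 0.2 | 1.625 | 48.5% |
| 0.3 | 2.437 | 77.8% |

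True mode effect of 0.3 SD, worsening from other causes:

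| Drift | Net mean | Rejection |
|---|---|---|
| 0 | 0.3 | 77.8% |
| −0.1 | 0.2 | 48.5% |
| −0.2 | 0.1 | 20.0% |

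A larger sample makes the false attribution more likely. With n = 150 (assumed) and no mode effect, improvements of 0.1 and 0.2 SD give rejection in 33.5% and 78.6% of trials.

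**3. What could the scheduled data add?** Section 6.6 schedules blinded On-Medication scores with stimulation off and on at both visits. Write the on-stimulation change (month 3 minus month 6) as M + R + P, where M is mode, R is re-optimisation and P is change common to both stimulation states. The off-stimulation change is then P. The month-6 minus month-3 change in the off-minus-on difference equals the on-stimulation change minus the off-stimulation change:

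(M + R + P) − P = M + R.

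P drops out and R stays. This assumes that no stimulation effect persists into the off-stimulation score.

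Precision, assuming each change has SD 10 and correlation r: the SD of the contrast is √(2·100·(1−r)) = 14.1, 12.2 and 10.0 at r = 0, 0.25 and 0.5. Power for 3 points at n = 66 is then 52%, 63% and 78%. The direct comparison has 78% at SD 10, because 3/10 = 0.3.

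**The case against.** The strongest reply is that this is a secondary endpoint that gates nothing, in a study described as observational and without pass/fail criteria (12.3). Evaluator and subject are blinded, the comparison is within subject, and section 12.7 already plans the as-programmed and implant-timing subsets. Section 6.11 also promises stratified analysis to diagnose confounding, without limiting it to the primary endpoint. The figures above rest on assumed drift and show only that a t test responds to a shifted mean. All of this stands and limits the weight of the point. None of it separates mode from period, and the stated aim remains a comparison of modes.

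A reader might infer more about the population: that section 12.8 lets in subjects with only 4-channel leads, who cannot switch to directional stimulation and so dilute the effect. Section 6.6 says: "Subjects who are implanted with the 4 channel lead will only have the omnidirectional testing at the initial programming visit"; at month 3 they again have omnidirectional testing only. The documents do not establish that such subjects enter this analysis. Section 12.1 can be read as confining the report to subjects with evaluable windows in both modes, which excludes them and makes the dilution zero. The endpoint's own definition labels the month-6 score directional. The 4-channel share is not given. What stands is narrower: section 12.8 does not restate the both-modes condition for this endpoint.

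A reader might also infer that the detailed device testing at month 3 disturbs the UPDRS score at that visit. The order of testing and scoring is not stated, so this cannot be claimed.

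**Conclusion.** The attribution point holds, with high confidence, because it rests on the planned sequence and not on any assumed number. The test as written cannot show that directional stimulation itself has the greater therapeutic effect. It can show only that scores changed between month 3 and month 6.

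The size is unknown. If non-device drift is between 0.1 and 0.3 SD, the 5% error rate becomes 20% to 78% at n = 66, and drift the other way can mask a true effect. The documents do not show that such drift exists, so it would be wrong to conclude that the result will be biased by any given amount or in a known direction.

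The analysis-set point is minor and conditional: it is a missing cross-reference, with no demonstrated loss of power. The unnamed medication and stimulation state is a wording gap. On Medication is the only medication state scheduled at both visits, and On Stimulation is the only coherent choice for comparing modes.

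Overall this should be fixed, at modest severity. The within-visit comparison in the primary endpoint does not share the period problem.

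**What to change.** 1. In section 12.1.2.2, describe the result as the within-subject change from month 3 (planned omnidirectional) to month 6 (planned directional), On Medication/On Stimulation at both visits, and state that it is not attributable to directional stimulation alone.
2. Pre-specify as supportive the change between the two visits in the blinded On-Medication off-minus-on stimulation difference. State its limits: it removes only changes common to both stimulation states and not re-optimisation gains, it may be less precise, and it depends on a stimulation-off interval before scoring that the documents do not give.
3. In section 12.8, cross-reference for this endpoint the existing set with evaluable windows in both modes. Keep the as-programmed subset of section 12.7 as a sensitivity analysis. Also show the result in all subjects with both scores.

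A restriction to 8-channel leads would be looser than item 3. The selected contact on such a lead may be 1 or 4, while directional testing covers only contact 2 or 3, and the rule would have to say whether one or both leads count.

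Cost: no new data are needed. Section 12 is part of the CIP, so the amendment steps of section 14.0 apply. The claim becomes more modest and the supportive analysis may have less power, as shown. Section 12.4 plans interim comparisons of month-3 and month-6 UPDRS, so a change to the analysis set could look data-driven. Item 3 should therefore be recorded as a clarification, with its timing relative to those looks, and preferably made before the data freeze in section 12.12.
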